2.3. Safety Endpoints

Objectives	Endpoints

A secondary objective is to evaluate the safety and tolerability of TEV-50717.
	
The safety endpoints are as follows:
 
 • incidence of adverse events • observed values and changes from baseline in vital signs • observed values and change from baseline in the Children’s Depression Inventory Second Edition (CDI-2; Parent and Self-report Profiles) • observed values in the children’s Columbia Suicide Severity Rating Scale (C-SSRS) • observed values and changes from baseline in electrocardiogram (ECG) parameters and shifts from baseline for clinically significant abnormal findings • observed values and changes from screening in clinical laboratory parameters (hematology, chemistry, and urinalysis) 
In addition to routine monitoring of adverse events, clinical laboratory parameters, 12-lead ECGs and safety scales, an independent Data Monitoring Committee will monitor safety during the conduct of the study.

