7.8. Electrocardiography

A 12-lead ECG will be recorded at the time points detailed in [Table 2](#). All ECGs will be performed after at least 5 minutes rest in a supine or semi-supine position. A qualified physician at a central diagnostic center will be interpreting the ECG.

All ECG results outside of the reference ranges will be judged by the investigator as belonging to one of the following categories:

- abnormal and not clinically significant
- abnormal and clinically significant

Any ECG finding that is judged by the investigator as clinically significant (except at the screening visit) will be considered an adverse event, recorded on the source documentation and in the CRF, and monitored as described in [Section 7.1.2](#).

If a post-baseline QTcF value >500 msec or change from baseline >60 msec is found, the investigator should repeat the ECG assessment twice and compare the average of the 2 pre-treatment QTcF values (baseline and screening) to the average of the 3 post-baseline QTcF values. The IMP must be stopped for any confirmed post-baseline QTcF value >500 msec or increase from baseline >60 msec.

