## **9. Safety**

The safety endpoints for this study are as follows:

- Incidence of adverse events
- Observed values and changes from baseline in vital signs
- Observed values and change from baseline in the Children's Depression Inventory, Second Edition (CDI-2), Parent and Self-report Profiles
- Observed values in the Children's Columbia-Suicide Severity Rating Scale (C-SSRS)
- Observed values in electrocardiogram (ECG) parameters and shifts from screening for clinically significant abnormal findings
- Observed values and changes from screening in clinical laboratory parameters (hematology, chemistry, and urinalysis)

The safety analysis set will be used for all safety analyses. Summaries will be presented by treatment group and for all patients.

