### 9.9. ECG

Assessment of Standard 12-lead ECG are obtained at screening, baseline, weeks 4 and 8. A central ECG Standard 12-lead ECG will record heart rate (HR), PR interval, RR interval, QT interval, Frederica's corrected QT interval (QTcF), and QRS duration. The overall ECG assessment will be centrally reported as "Normal" or "Abnormal" with respect to relevant abnormalities. If a post-baseline QTcF value  $>$ 500 msec or change from baseline  $>$ 60 msec is found, the investigator should repeat the ECG assessment twice. In this case, the confirmed QTcF, defined as the average of all 3 ECG values at the visit, will be used for summary. If ECG tests are repeated on the same day for any other reason per investigators discretion, the average of all ECG values on that day will be used for summary.

This document is confidential.

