**Statistical Analysis Plan for Interventional Studies**

Sponsor: Teva Branded Pharmaceutical Products R&D, Inc./Nuvelution TS Pharma, INC.;  
Protocol No.: TV50717-CNS-30060

---

Observed results of each ECG parameter and change from baseline will be summarized by treatment and overall, and by visit using descriptive statistics.

In addition, for QTcF, average baseline confirmed QTcF (the average of the screening and Day 1 QTcF), and the change from average baseline will be summarized by treatment and overall, and by visit using descriptive statistics.

QTcF values will be classified as having QTc prolongation according to the following conditions.

QTc Prolongation
Confirmed QTcF >450 msec
Confirmed QTcF >480 msec
Confirmed QTcF >500 msec
Increase from baseline QTcF $\geq$ 60 msec
Increase from average baseline confirmed QTcF $\geq$ 60 msec
Increase from baseline QTcF $\geq$ 30 msec
Increase from average baseline confirmed QTcF $\geq$ 30 msec

The number and percentage of patients with QTc prolongation will be summarized by treatment and overall, and by visit.

A shift table comparing the overall ECG assessment from baseline to each visit will be presented.

In addition, the abnormal post-baseline ECG results will also be summarized for patients with at least one abnormal value during the treatment period. The summary will be completed by treatment and overall, and age groups (6 - < 8 years, 8 - < 12 years, and 12 - < 16 years), and overall using the age at the time of the individual assessment.

Criteria for abnormal values used in the study are presented in [Table 6](#).

This document is confidential.

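### The ECG safety endpoint is a shift for clinically significant abnormal findings, but the only ECG shift table in the legible SAP text uses a central Normal/Abnormal read that cannot show it, and the SAP's reference visit is inconsistent.

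*SAP*

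**What the plan says.** **Endpoint.** Protocol 2.3 lists, besides ECG values and their changes, "shifts from baseline for clinically significant abnormal findings". SAP 4.5 and SAP 9 carry the same idea with a different reference visit: "shifts from screening for clinically significant abnormal findings".

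**Who judges clinical significance.** Protocol 7.8 gives this to the investigator: "All ECG results outside of the reference ranges will be judged by the investigator as belonging to one of the following categories", namely abnormal and not clinically significant, or abnormal and clinically significant. The same section makes a clinically significant ECG finding after screening an adverse event, to be entered in the CRF.

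**Analysis.** SAP 9.9 describes a different variable. "The overall ECG assessment will be centrally reported as" Normal or Abnormal, with respect to relevant abnormalities, a term the SAP does not define. The shift table is built on that variable: "A shift table comparing the overall ECG assessment from baseline to each visit will be presented".

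**Other ECG outputs in SAP 9.9.** These are descriptive statistics by visit, counts of QTcF above set limits and of QTcF increases, and heart rate, PR and QRS values outside the age-specific limits of SAP Table 6. None uses the investigator's judgement of clinical significance.

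**The concern.** A shift table cross-classifies each child's status on treatment against status before treatment. To show shifts to clinically significant findings, the status variable needs a clinically significant category. The planned variable has none, so a programmer who follows SAP 9.9 exactly will not produce the endpoint that both documents name. The visible text of SAP 12 lists only a new exploratory endpoint as a change from the protocol, so the difference does not read as a deliberate change.

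The second problem is the reference visit. SAP 9.9 has ECGs taken at both screening and baseline, so a shift from screening and a shift from baseline are different comparisons. The SAP names one in its endpoint lists and the other in its analysis.

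At stake is a by-arm display of a named paediatric safety endpoint, not an efficacy conclusion.

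**Working it through.** The plan gives no figure to reproduce here, so the check is to map the endpoint's categories onto the planned table.

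Let N be normal, NCS abnormal and not clinically significant, and CS abnormal and clinically significant. Baseline and on-treatment status give 3 × 3 = 9 combinations. Assume that the central reader and the investigator agree on normal versus abnormal. Collapsing to the SAP's 2 × 2 table gives:

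| Planned cell | Combinations it contains | Number |
|---|---|---|
| Normal to Normal | N→N | 1 |
| Normal to Abnormal | N→NCS, N→CS | 2 |
| Abnormal to Normal | NCS→N, CS→N | 2 |
| Abnormal to Abnormal | NCS→NCS, NCS→CS, CS→NCS, CS→CS | 4 |

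The total is 1 + 2 + 2 + 4 = 9.

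Two combinations are shifts to a clinically significant finding:

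- N→CS shares its cell with N→NCS, so a new clinically significant finding cannot be told from a new minor one.
- NCS→CS falls in Abnormal to Abnormal, where no shift appears.

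No cell isolates a shift to CS. That follows from the number of levels and does not depend on how many children are abnormal at baseline. If the central read and the investigator disagree on what is abnormal, the planned table is further still from the endpoint.

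The reference visit, side by side:

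| Place | Reference visit for the ECG shift |
|---|---|
| Protocol 2.3 | baseline |
| SAP 4.5 and 9, ECG bullet | screening |
| SAP 9.9, shift table | baseline |

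The SAP contradicts itself, and its endpoint lists contradict the protocol.

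For comparison, SAP 9.11 sets out the neurological examination in the three categories that the ECG endpoint needs, so the structure is already in use in this SAP.

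**The case against.** The strongest reply is that little safety information is lost. Under Protocol 7.8 a post-screening ECG finding judged clinically significant is an adverse event, and SAP 9.4 summarises treatment-emergent events by arm, by system organ class and preferred term, by severity and by period. The exclusion criteria in Protocol 4.2 remove children with prolonged QTcF at screening or a history of congenital long QT syndrome, bradyarrhythmia or uncompensated heart failure. Clinically significant findings at baseline should therefore be uncommon, and by-arm incidence of new ones carries most of what the shift would show. This stands, and it limits the consequence. It does not remove the mismatch, because adverse event tables do not cross-classify on-treatment ECG status against baseline status.

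It is also fair to say that the gap is not the SAP's alone. Protocol 9.7.1 plans counts and percentages of abnormal ECG findings and QTcF categories, without a shift by clinical significance. The protocol's endpoint list and its analysis section already differ, and SAP 9.9 follows the latter and adds a shift table.

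Three stronger readings are tempting and are not supported:

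- *A reader might infer that a countable group of children, those abnormal at baseline, is masked.* The documents give no rate of abnormal reads at baseline and no rate of worsening from NCS to CS. Nor is the limitation confined to that group: a two-level table cannot show a shift to CS for any child.
- *A reader might infer that a child who goes from a trivial to a significant abnormality always shows no shift.* That holds only if the central reader called the trivial finding Abnormal. The undefined restriction to relevant abnormalities might make it Normal.
- *A reader might infer that no such table exists anywhere.* The SAP's index of tables is redacted, so a further table cannot be excluded. The point is confined to the legible text.

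**Conclusion.** The mismatch is real and should be corrected. As written, SAP 9.9 does not produce the shift for clinically significant ECG findings that Protocol 2.3 and SAP 4.5 and 9 name, and the SAP is inconsistent on the reference visit.

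The consequence is limited: other by-arm summaries cover most of the same ground, and the analysis is descriptive. No count of affected children can be derived from the documents, so none is given.

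The conclusion on the table rests on two things: the legible SAP text being the whole specification, and the overall ECG assessment in the shift table being the central two-level read defined earlier in the same section. The conclusion on the reference visit rests only on the wording and holds either way.

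**What to change.** 1. In SAP 9.9, add a shift table by arm with three levels (normal, abnormal not clinically significant, abnormal clinically significant), taken from the investigator classification in Protocol 7.8. Run it from the baseline defined in SAP 6.2.1 to each visit. Keep the central Normal/Abnormal table as supportive.
2. Before finalising this, confirm that the classification is in the database. Protocol 7.8 states CRF entry only for clinically significant findings, and Protocol Appendix S says that externally processed data are generally not transcribed to the CRF. If the not-significant category was not captured, use clinically significant yes/no.
3. In SAP 4.5 and SAP 9, change screening to baseline in the ECG bullet only. The laboratory bullet in both lists also says screening and should stay: it matches Protocol 2.3, and SAP 9.5 schedules laboratory tests only at screening and week 8, apart from week 9 repeats.

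The cost is one extra descriptive table, a one-word edit in two places, and the database check. No new assessment of patients is needed.

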**Table 6: Criteria for Abnormal ECG Parameters by Age**

ECG parameter (unit)	Age (years old)	Abnormally Low	Abnormally High
HR (bpm)	6 to <8	< 65	> 115
	8 to <12	< 55	> 110
	12 to <16	< 50	> 105
	≥16	< 50	> 100
PR interval (msec)	6 to <8	--	> 160
	8 to <12	--	> 175
	12 to <16	--	> 180
	≥16	--	> 200
QRS interval (msec)	6 to <8	--	> 100
	8 to <12	--	> 105
	12 to <16	--	> 110
	≥16	--	> 120

**9.10. Physical Examinations**

Physical examinations are performed obtained at screening and Week 8. Physical examinations will not be summarized. Physical examinations will be listed.

**9.11. Neurological Examinations**

Neurological examinations will be performed at screening and Week 8. Each assessment (i.e. Mental Status, Cranial Nerves, Motor System, Gait and Balance, Tendon Reflexes, Sensation and Other) will include category of normal/abnormal and not clinical significant (NCS)/abnormal and clinical significant (CS). Neurological examinations will be listed.

**9.12. ADHD Symptoms**

Based on input from the TEV-50717 Tourettes Syndrome Scientific Advisory Board (SAB) , which contains experts in the area of child psychiatric, and in the attempt to identify possible symptoms consistent with ADHD symptomatology, the items below from C&A-GTS-QOL were chosen:

[REDACTED]

[REDACTED]

[REDACTED]

This document is confidential.

[REDACTED]

[REDACTED]

[REDACTED]

[REDACTED]

Summary statistics will be provided to the observed values and change from baseline. This analyses are only exploratory and for signal detection purpose.

**9.13. Children’s Depression Inventory, Second Edition (CDI-2)**

The CDI-2 (parent and self-report versions) is administered at screening, baseline, and weeks 2, 4, 8, and 9. As the CDI-2 is designed for children 7 to 17 years of age, children 6 years of age at baseline will not complete the Self-report version; the caregiver/adult will complete the Parent version.

The CDI-2 self-report is a 28-item self-report questionnaire assessing depressive symptoms in children 7 to 17 years of age with basic reading and comprehension skills. In the CDI-2, children are asked to choose 1 of 3 statements that most closely aligns with their feelings in the previous 2 weeks. The CDI-2 Self-report version contains 6 subscales (emotional problem, negative mood/physical symptoms, negative self-esteem, functional problems, ineffectiveness, interpersonal problems). The raw score is the sum of all subscales scores, ranging from 0 to 56, with higher score indicating more severe depressive symptoms. The raw score is normalized to T-score (range: 40-90) based on patient’s age and gender.

The CDI-2 parent is a 17-item questionnaire administered to parents to assess depression-related behaviors observed in their children. In the CDI-2 Parent, parents are asked to rate their child’s behaviors in the past 2 weeks on a 4-point Likert scale from “not at all” to “much or most of the time”. The CDI-2 parent version contains 2 subscales (emotional problems and functional problem). The raw score is the sum of the 2 subscales, ranging from 0 to 51, with higher score indicating more depression-related behaviors observed in their children.

The CDI-2 parent version and self-report versions subscale scores, raw scores, and self-report version T scores will be presented at baseline and each visit each is measured.

**9.14. Columbia-Suicide Severity Rating Scale (C-SSRS)**

The C-SSRS children’s baseline/screening scale assesses past and current suicidal ideation and behaviors to determine suicide risk and is administered at screening. The C-SSRS children’s since last visit (SLV) scale is administered at baseline and at weeks 2, 4, 8, and 9. Patients will be placed into categories for suicidal ideation and for suicidal behavior based on their responses to various questions.

The suicidal ideation categories will be determined as follows by examining the response to the 5 questions under Suicidal Ideation.

This document is confidential.

**Statistical Analysis Plan for Interventional Studies**

Sponsor: Teva Branded Pharmaceutical Products R&D, Inc./Nuvelution TS Pharma, INC.;  
 Protocol No.: TV50717-CNS-30060

Type	Section
Suicidal ideation	
(0) None – if response is No to Questions 1 and 2
 
(1) Wish to be Dead – if response to Question 1 is Yes and responses to Questions 2-5 are No.
 
(2) Non-Specific Active Suicidal Thoughts – if response to Question 2 is Yes and response to Questions 3-5 are No.
 
(3) Active Suicidal Ideation with Any Methods (Not Plan) without Intent to Act – if response to question 3 is Yes and response to questions 4 and 5 are No.
 
(4) Active Suicidal Ideation with Some Intent to Act, without Specific Plan – if response to Question 4 is Yes and response to Question 5 is No.
 
(5) Active Suicidal Ideation with Specific Plan and Intent – if response to Question 5 is Yes.

For suicidal behavior, the following categories will be used. The categories will be determined based on the response to the questions under suicidal behavior.

Type	Section
Suicidal behavior	
(6) Preparatory Acts or Behavior – if response to Preparatory Acts and Behavior is Yes and responses to Actual Attempt, Interrupted Attempt, Aborted Attempt, and Completed Suicide are No
 
(7) Aborted Attempt – if response to Aborted Attempt is Yes and responses to Actual Attempt, Aborted Attempt, and Completed Suicide are No.
 
(8) Interrupted Attempt – if response to Interrupted Attempt is Yes and response to Aborted Attempt, and Completed Suicide are No.
 
(9) Actual Attempt – if response to Actual Attempt is Yes and Completed Suicide is No.
 
(10) Completed Suicide - if response to Completed Suicide is Yes
 
(0) None – if responses to all the above 4 questions are No.

Suicidal ideation or behavior will be derived as the highest suicidal ideation or behavior score at the visit. Score of 0 represent “No Suicidal Ideation/Behavior”.

The frequency and percentage of suicidal ideation, suicidal behavior, suicidal ideation or behavior, and self-injurious behavior without suicidal intent will be summarized by treatment and overall, and visit. For baseline/screening version at baseline, past 2 years scores will be summarized.

Frequency and severity of suicidal ideation or behavior will also be summarized, using a shift table to examine changes in above C-SSRS scores from baseline compared to the worst (highest) category during the treatment period, by treatment and overall.

This document is confidential.

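### The SAP's C-SSRS rule for an aborted suicide attempt contradicts itself, so an aborted attempt without an actual attempt or completed suicide gets no positive behavior category

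*SAP*

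**What the plan says.** SAP Section 9.14 defines six suicidal-behavior codes from five items: preparatory acts, aborted attempt, interrupted attempt, actual attempt and completed suicide.

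- Category 6 (preparatory acts) needs that item Yes, and "responses to Actual Attempt, Interrupted Attempt, Aborted Attempt, and Completed Suicide are No".
- Category 7 (aborted) applies "if response to Aborted Attempt is Yes and responses to Actual Attempt, Aborted Attempt, and Completed Suicide are No".
- Category 8 (interrupted) applies "if response to Interrupted Attempt is Yes and response to Aborted Attempt, and Completed Suicide are No".
- Category 9 (actual) applies "if response to Actual Attempt is Yes and Completed Suicide is No".
- Category 10 (completed) applies "if response to Completed Suicide is Yes".
- Category 0 (none) applies "if responses to all the above 4 questions are No", although five items stand above it.

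Three outputs use these codes: the frequency of each behavior by visit and treatment; a combined score ("Suicidal ideation or behavior will be derived as the highest suicidal ideation or behavior score at the visit"); and a comparison of baseline with the treatment period, "using a shift table to examine changes in above C-SSRS scores from baseline compared to the worst (highest) category during the treatment period". Observed C-SSRS values are a listed safety endpoint (SAP Sections 4.5 and 9). The section is not redacted, and no other visible part of the SAP corrects the rules.

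**The concern.** The codes run from 6 to 10 in rising severity, and a child should take the code of the worst behavior reported. Categories 6 and 9 follow that pattern: each excludes every more severe behavior and nothing else. Categories 7 and 8 do not. Category 7 excludes the behavior it is meant to capture. Category 8 excludes a less severe behavior (aborted) and omits a more severe one (actual).

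An aborted attempt is one of the events this scale is used to detect. Protocol Section 7.2.2 names it as a separate behavior needing immediate evaluation, and Section 7.9 explains why suicidality is monitored with this drug. Exclusion criteria e and f (Protocol Section 4.2) bar children with any previous actual, interrupted or aborted attempt, or with preparatory acts within 2 years. Behavior at baseline should therefore be 0 in eligible children, and a new aborted attempt on treatment should appear in the shift table as 0 to 7. Under the written rules that cell cannot be filled. With about 50 children per arm and such events expected to be rare, one lost case changes what the table shows.

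**Working it through.** No planned figure needs reproducing; the check is logical. Five Yes/No items give 2^5 = 32 response patterns. Write P, Ab, In, Ac, Co for preparatory, aborted, interrupted, actual and completed.

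**Step 1. Apply the rules as written.** An item that a rule does not mention is free and doubles the count.

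| Code | Condition as written | Patterns |
|---|---|---|
| 0 | all five No (the reading that covers every item) | 1 |
| 6 | P Yes; Ab, In, Ac, Co No | 1 |
| 7 | Ab Yes; Ac, Ab, Co No | 0 (impossible) |
| 8 | In Yes; Ab, Co No | 2 × 2 = 4 |
| 9 | Ac Yes; Co No | 2 × 2 × 2 = 8 |
| 10 | Co Yes | 2^4 = 16 |

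The assignments total 1 + 1 + 0 + 4 + 8 + 16 = 30.

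**Step 2. Find overlaps.** Codes 8 and 9 both apply when In and Ac are Yes and Ab and Co are No, with P free: 2 patterns. Distinct patterns covered: 30 − 2 = 28.

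**Step 3. Find gaps.** 32 − 28 = 4 patterns have no code: Ab alone; P + Ab; Ab + In; P + Ab + In. These are all the patterns with an aborted attempt, no actual attempt and no completed suicide. No other rule picks them up: codes 6 and 8 require Ab No, code 9 requires Ac Yes, and code 10 requires Co Yes. Among the 2^4 − 1 = 15 patterns with at least one Yes and no completed suicide, 4 are lost and 2 are double-coded.

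**Step 4. Test the wording of category 0.** The text does not say which four of the five items are meant. If Ab is the one left out, a child whose only behavior is an aborted attempt is coded 0, that is, no suicidal behavior. If any other item is left out, a child with only that behavior still meets its own positive code, and the aborted-only child stays uncoded.

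**Step 5. Correct category 7 alone** (Ab Yes; In, Ac, Co No). Code 7 then holds 2 patterns. Ab + In and P + Ab + In remain uncoded, because category 8 still demands Ab No. The 2 double-coded patterns also remain.

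**Step 6. Correct categories 7 and 8** (category 8: In Yes; Ac, Co No), with category 0 over all five items. Codes 0, 6, 7, 8, 9 and 10 hold 1, 1, 2, 4, 8 and 16 patterns. The sum is 32, with no gaps and no overlaps.

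**The case against.** The strongest reply is that this is a drafting slip with limited reach. Several parts of it stand.

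- An aborted attempt accompanied by an actual attempt or completed suicide is still coded, as 9 or 10.
- The event should be seen elsewhere. Protocol Section 7.9 has the investigator record suicidality as an adverse event, SAP Section 9.4 tabulates a suicide/self-injury SMQ, and SAP Section 6.1 puts all visit assessments in the listings.
- Clinical follow-up under Protocol Section 7.2.2 acts on the reported behavior and does not use these codes.
- For the 2 double-coded patterns, taking the highest value gives 9 in the combined score and the shift table. Only the behavior-only frequencies by visit are left with a double count.
- Pattern counts measure the gap in the rules and say nothing about how many children would be affected. Eligibility criteria make such events uncommon, treatment lasts 8 weeks, and the output is descriptive.

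None of this puts the missing event back into the C-SSRS tables. An adverse-event count that disagrees with the C-SSRS table would itself need explaining. Nor is it safe to rely on a programmer noticing. The SAP is the specification, the impossible line 7 is the conspicuous error, and Step 5 shows that mending it alone leaves half of the 4 gaps open.

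**Conclusion.** The concern holds. Followed literally, SAP Section 9.14 leaves category 7 empty in all arms, gives no positive behavior code to 4 of 32 response patterns, and gives two codes to 2 more. A child in one of the 4 uncoded patterns would appear in the combined score at the ideation value, which is at most 5, or as missing; the SAP does not say which. On one reading of category 0, a child with only an aborted attempt would be coded as having no suicidal behavior.

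The effect is confined to the derived C-SSRS summaries: the behavior frequencies, the combined score and the shift table. Efficacy, power and type I error are untouched. The number of children affected cannot be stated in advance and may be zero. The intended wording of categories 7 and 8 is inferred from the ordering 6 to 10 and from the pattern in categories 6 and 9. Because following the written rule gives a wrong result for a listed safety endpoint in a pediatric trial, it should be corrected before unblinding.

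**What to change.** Amend three lines of SAP Section 9.14:

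- Category 7: aborted attempt Yes; interrupted attempt, actual attempt and completed suicide No.
- Category 8: interrupted attempt Yes; actual attempt and completed suicide No.
- Category 0: No to all five behavior items, named individually.

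Derive the behavior frequencies, the combined score and the shift table from the corrected codes, and add a program check that each complete set of responses maps to exactly one behavior code. The cost is three lines of text and the matching derivation code, with no new data. Under Protocol Section 9, a change made after the SAP is final should also be disclosed in the clinical study report.
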